Statistical Analysis Plan

NCT04175106

Date: 25-Oct-2020

1 Methodology

This methodology section covers the study design, which is a crossover longitudinal study. Measurements are taken for each subject across time and treatment. First, the study design is described in detail, common methodology for crossover and longitudinal studies is presented, and then a statistical analysis methodology blending the two is proposed.

1.1 Study design

A four-way, placebo-controlled crossover study will be conducted to compare phytonutrient bioavailability from two varieties of blueberries, blueberry-rich protein bar, and a placebo drink. Each of the 28 participants will partake in a three-month long study with four feeding visits, separated by washout periods lasting 7 days, ranging from 11 to 18 days. For each visit, participants will provide blood (baseline, 1, 3, 6, 9, 24, 48 hours) and urine (48 hours prior, 24 hours prior, 0-9 hours, 9-24 hours, 24-48 hours) samples to be analyzed for biomarkers necessary to measure bioavailability and other pharmacokinetic parameters. Figure 1 illustrates the steps a participant takes for one feeding visit. The study has been reviewed and approved by the Institutional Review Board at the North Carolina State University.

[figure not shown]

Figure 1: Guideline of Dietary Restrictions of Prior and During the study

1.2 Methodology For Longitudinal Studies

Longitudinal studies involve repeated measurements of specified variables over a period of time. Within each period k , each subject i will undergo 7 blood collections at time points of 0, 1, 3, 6, 9, 24, and 48 hours post-treatment and 5 urine collections at -48, -24 pre-intervention and 0-9, 9-24 and 24-48 hours post-treatment tracking concentrations of pre-specified metabolites reported as concentration versus time. Concentrations will be converted to corresponding pharmacokinetic parameters: maximum serum concentration (C_{max}), time at maximum concentration (T_{max}), the half-life [$t_{1/2}$], the area under the curve (AUC), area under the first moment curve (AUMC), the clearance (CL), the volume of distribution (V_d), and the mean residence time (MRT) of blueberry-derived metabolites in the blood and urine using an appropriate pharmacokinetic model (PK) [BAMStudy2020]. The software Phoenix WinNonlin is planned to be used to fit the PK model. Using the calculated AUC and dosage D, the total bioavailability for each metabolite can be determined [2]. Subject specified covariates (such as gender, age, body mass index, treatment order, and sample type) may be significant in the PK

model and will be considered for potential inclusion. However, the exact nature of this model will be determined as the study is completed and is beyond the scope of this statistical analysis plan.

1.3 Methodology for Crossover Studies

In crossover studies, measurements are repeated across treatments. Each subject receives each treatment with a washout period in between. We will use a toy example where Y_{ijkl} is the outcome, i denotes the subject, j denotes the treatment, k denotes the period, and l denotes the sequence. For four treatments, A, B, C, D, there are a number of different treatment sequences (e.g. ABCD, ACDB, BACD) and four periods. We account for variability from sequences and periods in the model. An example of a crossover model is the following:

$$Y_{ijkl} = \mu + \delta_l + \beta_{i(l)} + \alpha_j + \gamma_k + \alpha_{j|k} + \varepsilon_{ijkl} \quad (3.1)$$

where, μ is the overall mean, fixed sequence effect is δ_l , fixed treatment effect is α_j , fixed period effect is γ_k , and $\beta_{i(l)}$ is the random individual subject effect for individual i nested in the sequence l . The fixed interaction between treatment and period is $\alpha_{j|k}$ and the random error from the realization process or measurement error is ε_{ijkl} . For the random effects, we assume $\beta_{i(l)}$ is independent of ε_{ijkl} and we have flexibility in modeling the random errors. For example, it may be reasonable for the residual error to have different variances based on treatment: $Var(\varepsilon_{i1kl}) \neq Var(\varepsilon_{i2kl})$. Naturally, one could add additional fixed effects for covariates or interactions between covariates and treatments. Mean and covariance parameters are typically estimated through maximum likelihood estimation (MLE). In SAS, PROC MIXED is a popular procedure to fit these mixed effects models. Sophisticated inference including adjustments for multiple comparisons can be carried out with PROC MIXED. In R, the nlme and lme4 [1] packages can be used to fit the models. The lmerTest package is a popular companion to lme4 for statistical inference [3].

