1.4 Proposed Methodology for Crossover Longitudinal Studies

The model specified in (1.1) will serve as a framework for testing the differences of fixed effects between treatments. Using the methodology outlined in Section 1.2, the appropriate PK parameters for a given metabolite (ex. Bioavailability) will be calculated. The PK parameters will be represented as the continuous responses Y_{ijkl} in the model. Note that each measured PK parameter is specified to a given subject I receiving treatment j at a specified period k within sequence l .

It is of primary interest to test the potential differences in bioavailability of blueberry-derived metabolites across treatments. Given the number of metabolites being tested, multiple comparison adjustments will be necessary. There are a multitude of strategies for tackling such problems each with their respective advantages and disadvantages. However, given the relatively small sample size ($n=28$), controlling the family-wise error rate (FWER) across all metabolites

may drain requisite statistical power needed to detect any difference between treatments. It may be beneficial to set up a smaller subset of metabolites prior to analysis that are of primary interest and then investigate differences between the remaining metabolites in an exploratory nature.

[figure not shown]
2 Recommended Analysis/Design

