2.2 Fitting the Model

The toy dataset provided serves to illustrate the proposed methodology of the actual analysis. The dataset contains PK parameters from 15 subjects participating in a crossover design study with three periods and two treatment groups, a blueberry treatment and a control group. At each period, subjects had concentrations of 15 different metabolites measured via blood and urine samples. Concentrations were converted to corresponding pharmacokinetic parameter using an appropriate PK model. The primary purpose of the study was to compare the bioavailability of the ten metabolites between the blueberry treatment and the control group.

We propose the following model for analysis:

$$Y_{ijkl}^n = \mu + \delta_l^n + \alpha_j^n + \gamma_k^n + (\alpha\gamma)_{jk}^n + \varepsilon_{ijkl} \quad (2.1)$$

Below are detailed descriptions of each term in the model:

- μ : Overall mean.
- δ_l^n : Sequence Effect for metabolite n .
- α_j^n : Fixed treatment effect for metabolite n .
- γ_k^n : Period effect for metabolite n .
- $\alpha\gamma_{jk}^n$: Interaction between treatment and period for metabolite.
- ε_{ijkl} : Random error from the realization process or measurement error.

The effects δ_l^n , γ_k^n , and $\alpha\gamma_{jk}^n$ can be considered fixed or random. We assume the random effects are independent of each other. Here the response Y_{ijkl} , represents the bioavailability of metabolite n . Additionally, i denotes the i -th subject in the dataset. If we are interested in the model for just one metabolite, we can subset the dataset to just include observations for that one metabolite and then fit a similar, smaller model. An example is:

$$Y_{ijkl} = \mu + \delta_l + \alpha_j + \gamma_k + \varepsilon_{ijkl} \quad (2.2)$$

Below are detailed descriptions of each term in the model:

- μ : Overall mean.
- δ_l : Sequence Effect.
- α_j : Fixed treatment effect.
- γ_k : Period effect.
- ε_{ijkl} : Random error from the realization process or measurement error.

Notice this is the same model as before without the interaction, but without the n superscripts, since we only have one metabolite of interest.

This model can be fit using the `lmer` function in the `lme4` package of R. We will use the smaller model with just one metabolite for demonstration. To add the effect of one variable, `X_1`,

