2.3 Interpreting Model Output

Using the lmerTest package in R, we can conduct hypothesis tests for fixed and random effects in linear mixed effects models. The anova function provides F-tests on the fixed effects, letting you evaluate if a fixed effect is useful for explaining the response. Using the above model, the anova output is as follows:

```
> anova(fit)
Type III Analysis of Variance Table with Satterthwaite's method
  Sum Sq Mean Sq NumDF DenDF F value    Pr(>F)
Treatment  158.70 158.70     1 177.99 17.746 4.005e-05 ***
'Visit Period' 391.38 195.69     2 178.34 21.883 3.170e-09 ***
---
Signif. codes:  0 '***' 0.001 '**' 0.01 '*' 0.05 '.' 0.1 ' ' 1
```

Based on this, we can see that both treatment and period are useful for explaining the response. Since treatment is binary (control, treatment) here, we can examine if administering the treatment increases or decreases the response, on average. The summary function is one way to do this. Below is selected output:

```
> summary(fit)
Fixed effects:
  Estimate Std. Error    df t value Pr(>|t|)    
(Intercept)  0.02752  0.84451 4.24374  0.033  0.975
TreatmentTreatment 1.91665  0.45498 177.99167  4.213 4.00e-05 ***
'Visit Period'B -0.29409  0.55514 178.22795 -0.530  0.597
'Visit Period'C  3.24513  0.63618 178.66646  5.101 8.57e-07 ***
```

Notice the estimate for the TreatmentTreatment is 1.91665. This indicates the model the model estimates a 1.91655 increase in AUC if the Treatment is administered instead of the control. The corresponding p-value is small, so we can be confident that the treatment increases AUC, on average. To check if the random effects are useful for explaining the response. Since we are not interested in specific levels of the random effects, we just want to check if considerably variation is coming from the random effects. The ranova function runs a hypothesis testing the variance against zero. For the ANOVA model, here is the output:

```

> ranova(fit)
ANOVA-like table for random-effects: Single term deletions

Model:
AUC48 ~ Treatment + 'Visit Period' + (1 | seq)
      npar  logLik   AIC   LRT Df Pr(>Chisq)
<none>      6 -454.87 921.74
(1 | seq)    5 -460.85 931.70 11.969  1  0.000541 ***
---
Signif. codes:  0 '***' 0.001 '**' 0.01 '*' 0.05 '.' 0.1 ' ' 1

```

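### The proposed model (2.1) combines sequence with a treatment-by-period interaction and omits the participant effect, so its default treatment coefficients can be aliased or reduced to an imprecise period-1 contrast

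*SAP*

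**What the plan says.** SAP 1.3 gives an example crossover model, numbered (3.1), with treatment and period effects, a random participant effect nested in sequence, and two further fixed terms. One is sequence ("where, μ is the overall mean, fixed sequence effect is" the first term defined). The other is treatment-by-period ("The fixed interaction between treatment and period is" the last).

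SAP 1.4 then states: "The model specified in (1.1) will serve as a framework for testing the differences of fixed effects between treatments". No equation with that number appears in the text; (3.1) is the natural candidate.

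SAP 2.2 puts forward model (2.1) for the analysis. It has sequence, treatment, period and an interaction term described as "Interaction between treatment and period for metabolite". It has no participant term. Sequence, period and interaction "can be considered fixed or random".

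A smaller model (2.2) follows as an example for a single metabolite: "Notice this is the same model as before without the interaction". The printed fit in SAP 2.3 is of this smaller model: "AUC48 ~ Treatment + 'Visit Period' + (1 | seq" closes the formula. SAP 2.3 tests treatment with an F-test and then turns to the size and direction of the effect: "The summary function is one way to do this".

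Neither document lists the treatment orders. SAP 1.3 gives three orders as examples only.

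**The concern.** In a four-period crossover, each treatment difference should come from within-participant comparisons averaged over the four periods. Two features of (2.1) work against this.

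First, treatment-by-period and sequence carry overlapping information. With few orders, part of the interaction is the sequence effect, and the full model cannot be fitted.

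Second, once a fixed interaction is in the model, R's default coding makes each treatment line of `summary()` the difference from the reference treatment in the first period only. An analyst who fits (2.1) and reads treatment effects as SAP 2.3 illustrates would report that quantity. The SAP does not warn of this and defines no period-averaged contrast.

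At stake is the precision of the primary comparison in a trial of 28 participants, where SAP 1.4 already worries about power. Two analysts following the SAP could also report different treatment effects from the same data.

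**Working it through.** **1. The plan's own output.** From SAP 2.3:
- t = 1.91665 / 0.45498 = 4.2126, and t² = 17.746, equal to the printed F.
- AIC = 2 × 454.87 + 2 × 6 = 921.74, as printed.
- The 6 parameters are intercept 1 + treatment 1 + period 2 + sequence variance 1 + residual variance 1. A fixed interaction would add 2 and give 8.

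So the printed coefficient comes from a model without the interaction.

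**2. Inputs for the four-treatment trial.** There are four treatments, four periods and 28 participants (SAP 1.1 and 1.3; protocol, participant numbers). Assumptions: complete balanced data; a random participant effect, as in (3.1); total variance 1; intraclass correlation ρ of 0.3, 0.5 or 0.7. The order set is also assumed, because the documents do not give it.

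**3. Estimability, sequence and interaction fixed.**
- One four-order square, 7 participants per order: 1 + 3 treatment + 3 period + 9 interaction + 3 sequence = 19 columns. The 4 × 4 = 16 treatment-period cells each occur in exactly one order, so the cell determines the sequence. Rank is 16, and 3 columns are aliased.
- All 24 orders: 1 + 3 + 3 + 9 + 23 = 39 columns, rank 39.

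In the four-order square the period-1 treatment coefficient is not estimable, so its value depends on which 3 columns are removed. If interaction columns go, the standard errors of the three treatment coefficients are 2.24, 1.41 and 1.41 times the additive model's in a Williams square, and 1.73, 2.00 and 1.73 times in a cyclic square. These ratios are the same at each ρ. If the sequence columns go, the result is the four-order fit without sequence shown in step 5.

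**4. Additive reference model** (treatment + period + sequence + random participant). The standard error of a pairwise contrast is √(2(1 − ρ)/28):
- ρ = 0.3: √0.0500 = 0.224
- ρ = 0.5: √0.0357 = 0.189
- ρ = 0.7: √0.0214 = 0.146

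**5. Default-coded treatment coefficient with a fixed interaction.** In a four-order square without fixed sequence, 16 parameters fit 16 cells. The coefficient is then the difference of two period-1 cell means from 7 different people each, with standard error √(2/7) = 0.5345 at every ρ. The variance ratio to the additive model is (2/7) ÷ (2(1 − ρ)/28) = 4/(1 − ρ).

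| Order set | Sequence | Variance ratio at ρ = 0.3 / 0.5 / 0.7 | SE ratio |
|---|---|---|---|
| Four-order square, n = 28 | not fixed | 5.71 / 8.00 / 13.33 | 2.4 / 2.8 / 3.7 |
| All 24 orders, n = 24 | fixed | 5.50 / 5.50 / 5.50 | 2.35 at each |
| All 24 orders, n = 24 | not fitted | 4.80 / 5.09 / 5.29 | 2.19 / 2.26 / 2.30 |

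Each ratio compares with the additive model at the same n. The 24-order rows use n = 24, the expected number of completers, so that the set is balanced.

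**6. Where the information comes from.** In the four-order square without fixed sequence, all the weight falls on period-1 values of different people, so the contrast is purely between-person. With all 24 orders and fixed sequence, the weights sum to zero within each participant, so the contrast is within-person but imprecise. With sequence not fitted it is mixed.

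**7. Period-averaged contrast.** Averaging the treatment difference over the four periods gives an estimable contrast in all these balanced cases, including the rank-deficient one. Its variance ratio to the additive model is 1.0.

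**The case against.** The strongest reply is that the SAP never applies `summary()` to (2.1). The demonstrated model has no interaction, and treatment is tested first by an F-test. The coefficient is then read because the toy treatment is binary, and the method is offered as one option. The trial has four treatments, so that reason does not carry over, and SAP 1.3 mentions software for multiple-comparison adjustment.

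This stands in one respect. A reader might infer that the printed 1.91665 is itself a period-1, between-person comparison. It is not, as the parameter count shows. The reply does not remove the concern, because (2.1) is the model put forward for analysis, (2.2) is called an example, and no other way of obtaining treatment contrasts is specified.

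A second reply is that the four-order square is assumed. That is correct. The example orders ABCD and ACDB share A in period 1, so they cannot belong to one Latin square, although they are only examples. When orders were drawn at random, the model was rank-deficient in 0.2% of 500 draws at n = 28 and 1.2% at n = 24. Aliasing is therefore a risk of a compact design, not a general result. The loss of precision does not need that design.

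A third reply is that (2.1) allows the interaction to be random, and then the coefficient is not tied to period 1. That also stands. But (3.1) calls the interaction fixed, and leaving the choice open in the primary model is a weakness in itself.

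A reader might also infer that the interaction discards the crossover whatever the orders, leaving a parallel-group comparison. The calculations do not support this. With all 24 orders and fixed sequence the contrast remains within-person, and the period-averaged contrast loses nothing.

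**Conclusion.** The concern holds in a conditional form. Models (3.1) and (2.1) combine sequence with treatment-by-period, and (2.1) also drops the participant effect.

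- If the orders form one balanced four-order square and both terms are fixed, 3 of the 9 interaction degrees of freedom are aliased with sequence, and the default treatment coefficients are arbitrary.
- If there are more orders, such as all 24, the model can be fitted. With a fixed interaction, the treatment line that `summary()` would give under (2.1) is a period-1 contrast with a standard error about 2.2 to 2.35 times the additive model's.
- In a four-order square without fixed sequence, that line is purely between-person, with ratios 2.4, 2.8 and 3.7 at ρ = 0.3, 0.5 and 0.7. These ratios belong to that full-rank fit, not to a fit that keeps sequence and drops 3 interaction columns.

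The figures rest on complete balanced data, a random participant effect added to (2.1), the assumed ρ, and assumed order sets. The toy output in SAP 2.3 is not in error on this point. The design loses nothing; the problem lies in the stated model and in how its coefficients would be read.

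**What to change.** - Replace (2.1) as the primary model with treatment, period and sequence as fixed effects and participant as a random effect, without treatment-by-period.
- Report all pairwise treatment contrasts as differences of period-averaged (marginal) means, not as `summary()` coefficients.
- Fit treatment-by-period only as a sensitivity analysis, without the sequence term, and again report period-averaged contrasts.
- State the set of treatment orders and how participants are allocated to them.
- Correct the equation reference in SAP 1.4 so that it names the primary model.

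The cost is SAP wording and a few lines of code. No new data are needed, and the treatment contrasts can be estimated under the additive model in every order set checked here.

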1.4 Proposed Methodology for Crossover Longitudinal Studies

The model specified in (1.1) will serve as a framework for testing the differences of fixed effects between treatments. Using the methodology outlined in Section 1.2, the appropriate PK parameters for a given metabolite (ex. Bioavailability) will be calculated. The PK parameters will be represented as the continuous responses Y_{ijkl} in the model. Note that each measured PK parameter is specified to a given subject I receiving treatment j at a specified period k within sequence l .

It is of primary interest to test the potential differences in bioavailability of blueberry-derived metabolites across treatments. Given the number of metabolites being tested, multiple comparison adjustments will be necessary. There are a multitude of strategies for tackling such problems each with their respective advantages and disadvantages. However, given the relatively small sample size ($n=28$), controlling the family-wise error rate (FWER) across all metabolites

may drain requisite statistical power needed to detect any difference between treatments. It may be beneficial to set up a smaller subset of metabolites prior to analysis that are of primary interest and then investigate differences between the remaining metabolites in an exploratory nature.

[figure not shown]
2 Recommended Analysis/Design

2.1 Exploratory Analysis

[figure not shown]
In this section, we will walk through a toy example to show how we could build a model similar to (1.1). In the subsequent section, we will build the model using the lme4 package in R and show how to conduct valid statistical inference using the lmerTest package in R.

For data manipulation, we mostly use the dplyr package and for plotting we mostly use the ggplot2 package. These are part of the “tidyverse” [4].

[figure not shown]
For this example, we will use AUC48 from the plasma dataset as our outcome. First, we examine the period effect using a boxplot.

Since the sequence variable is not already in the dataset, we need to create it. An example of creating the new variable is in the appendix.

Now, we are interested in which in the effect age may have on the response. We can examine this via a scatterplot.

A similar plot can easily be made for any other continuous covariate of interest. Based on these summary statistics, we can gain insight on what additional covariate we may want to include into the model.

2.2 Fitting the Model

The toy dataset provided serves to illustrate the proposed methodology of the actual analysis. The dataset contains PK parameters from 15 subjects participating in a crossover design study with three periods and two treatment groups, a blueberry treatment and a control group. At each period, subjects had concentrations of 15 different metabolites measured via blood and urine samples. Concentrations were converted to corresponding pharmacokinetic parameter using an appropriate PK model. The primary purpose of the study was to compare the bioavailability of the ten metabolites between the blueberry treatment and the control group.

We propose the following model for analysis:

$$Y_{ijkl}^n = \mu + \delta_l^n + \alpha_j^n + \gamma_k^n + (\alpha\gamma)_{jk}^n + \varepsilon_{ijkl} \quad (2.1)$$

Below are detailed descriptions of each term in the model:

- μ : Overall mean.
- δ_l^n : Sequence Effect for metabolite n .
- α_j^n : Fixed treatment effect for metabolite n .
- γ_k^n : Period effect for metabolite n .
- $\alpha\gamma_{jk}^n$: Interaction between treatment and period for metabolite.
- ε_{ijkl} : Random error from the realization process or measurement error.

The effects δ_l^n , γ_k^n , and $\alpha\gamma_{jk}^n$ can be considered fixed or random. We assume the random effects are independent of each other. Here the response Y_{ijkl} , represents the bioavailability of metabolite n . Additionally, i denotes the i -th subject in the dataset. If we are interested in the model for just one metabolite, we can subset the dataset to just include observations for that one metabolite and then fit a similar, smaller model. An example is:

$$Y_{ijkl} = \mu + \delta_l + \alpha_j + \gamma_k + \varepsilon_{ijkl} \quad (2.2)$$

Below are detailed descriptions of each term in the model:

- μ : Overall mean.
- δ_l : Sequence Effect.
- α_j : Fixed treatment effect.
- γ_k : Period effect.
- ε_{ijkl} : Random error from the realization process or measurement error.

Notice this is the same model as before without the interaction, but without the n superscripts, since we only have one metabolite of interest.

This model can be fit using the `lmer` function in the `lme4` package of R. We will use the smaller model with just one metabolite for demonstration. To add the effect of one variable, `X_1`,

we simple include it the model statement, $Y \sim X_1$, the first argument for the function. To specify a random effects, we use $(1|X_1)$ in the model statement. We can specify interactions with $X_1:X_2$. Below is specific example of model in 2.2, using AUC as the response, and treatment and period as fixed effects, and sequence as a random effect.

```

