## fit the model
## response: AUC48
## Fixed Effects: Treatment, Period
## Random Effects: Sequence
fit <- lmer(AUC48 ~ Treatment + (1|seq) +
  'Visit Period',
  data=dat, REML = FALSE)
```

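### The SAP's crossover model has a random participant effect, but the models proposed for analysis in SAP 2.2 and the only code have none

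*SAP*

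**What the plan says.** SAP 1.3 presents a crossover model numbered (3.1), introduced as an example. It contains a term that "is the random individual subject effect for individual i nested in the sequence". On the design it says only that "there are a number of different treatment sequences (e.g. ABCD, ACDB, BACD) and four periods"; the number of sequences used in this trial is not given.

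SAP 1.4 then states: "The model specified in (1.1) will serve as a framework for testing the differences of fixed effects between treatments". No equation in the SAP is numbered (1.1). Model (3.1) is the only one before that point.

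SAP 2.1 introduces what follows as a toy example. SAP 2.2, however, says "The toy dataset provided serves to illustrate the proposed methodology of the actual analysis" and continues "We propose the following model for analysis". Model (2.1) has sequence, treatment, period, treatment-by-period and error terms. Model (2.2) is the same without the interaction. In both, the subject appears only as an index, with no effect attached.

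The model is described as "using AUC as the response, and treatment and period as fixed effects, and sequence as a random effect". The call begins "fit <- lmer(AUC48 ~ Treatment + (1|seq", and that is its only random term. The same call is repeated in the Code Appendix.

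**The concern.** The protocol synopsis names within-participant variation as the primary outcome, and SAP 1.4 makes treatment differences in bioavailability the primary interest. A four-period crossover earns its precision by comparing each person with themselves, which a mixed model does through the participant effect. Without that effect, two values from one person are treated as no more alike than values from two people in the same sequence.

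Two consequences follow with one value per participant per period. Standard errors for the variety and processing comparisons become too large, so power is lost. Ordinary differences between people can also appear as a sequence effect, which is how SAP 2.3 reads its own output. SAP 1.4 is already worried about power at n = 28.

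An analyst who copies the only code supplied would fit the model without the participant.

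**Working it through.** **1. Which models contain a participant term**

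| Place | Participant term | Status in the SAP |
|---|---|---|
| (3.1), SAP 1.3 | Yes, random, nested in sequence | Example; apparently adopted by 1.4 as (1.1) |
| (2.1), SAP 2.2 | No | Proposed for analysis |
| (2.2), SAP 2.2 | No | Smaller single-metabolite version |
| Code, SAP 2.2 and appendix | No, `(1|seq)` only | Demonstration |

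**2. The printed output confirms the omission.** SAP 2.3 reports 6 parameters: intercept 1 + treatment 1 + period 2 + sequence variance 1 + residual variance 1 = 6. There is no room for a participant variance. The output is otherwise consistent:
- AIC = 2×6 + 2×454.87 = 921.74.
- The likelihood-ratio statistic is 2×(460.85 − 454.87) = 11.96 (printed 11.969), p = 0.00054.
- F = (1.91665/0.45498)² = 17.746.

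**3. Size of the standard-error distortion.** Inputs are 24 completers (protocol, participant numbers), 4 periods, complete data and no true sequence effect. The intraclass correlation (ICC) is assumed to be 0.3, 0.5 or 0.7; the documents give no value.

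Let L be the number of sequence labels and r = ICC/(1 − ICC), the between- to within-participant variance ratio. There are 24×4 = 96 values and 6 treatment and period parameters. Within labels, the residual sum of squares has expectation (in units of within-participant variance) (90 − L) + 4(24 − L)r. Maximum likelihood divides it by 96 − L when the sequence variance is estimated above zero. So

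reported SE / true SE ≈ √{[(90 − L) + 4(24 − L)r] / (96 − L)}

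- L = 4: √[(86 + 80r)/92] = 1.14, 1.34, 1.72. Simulation (20,000 trials per setting) gave mean ratios of 1.13, 1.33 and 1.70. By 24/ratio², the reported precision is that of about 18, 13 and 8 completers.
- L = 12: √[(78 + 48r)/84] = 1.08, 1.22, 1.50. This case is 24 orders labelled by the first two visits, as the appendix code would do.
- L = 24: √(66/72) = 0.957. The label coincides with the participant, and the small deficit comes only from maximum likelihood.

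**4. Power.** Take a true difference of 0.85 within-participant SD (assumed, not in the documents). The true SE is √(2/24) = 0.289 SD, so the difference is 0.85/0.289 = 2.94 standard errors. Simulated power at two-sided 5%:

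| Layout | ICC 0.3 | ICC 0.5 | ICC 0.7 |
|---|---|---|---|
| With participant effect (66 df) | 83% | 83% | 83% |
| As in 2.2, 4 sequences | 75% | 62% | 34% |
| As in 2.2, 12 labels | 78% | 69% | 50% |
| As in 2.2, independent random orders labelled by all four visits | 78% | 71% | 57% |
| As in 2.2, 24 distinct labels | 85% | 85% | 85% |

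For independent random orders the comparator with a participant effect is about 81%. With four sequences, type I error falls to 2.7%, 1.0% and 0.2%. With 24 labels it is about 6%, again from maximum likelihood.

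**5. Spurious sequence effects.** With no true sequence effect, the nominal 5% test of the sequence variance rejects 11%, 21% and 31% of the time with four sequences, and 43%, 72% and 88% with 12 labels.

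**6. Rows in the worked example.** Residual variance = 158.70/17.746 = 8.94. Ignoring the sequence variance, n ≈ 454.87/[0.5 ln(2π×8.94) + 0.5] = 180.9; allowing for it gives about 180. The treatment test has 177.99 denominator df. But 15 subjects × 3 periods = 45 subject-periods, so there appear to be about four rows for each, which the SAP does not explain. If the trial data were laid out that way, the error could reverse. With four rows per cell and assumed correlations, simulated type I error was about 15% without a participant effect, and 25% to 34% with a participant intercept alone.

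**The case against.** The strongest reply is that 1.4 governs and Section 2 is only a tutorial. Section 2 is headed as a recommendation, is called a toy example, and uses (2.2) for demonstration, while 1.4 says prospectively what will be done. That reading is possible, so it cannot be asserted that the sponsor will omit the participant. It does not remove the conflict. SAP 2.2 says that it proposes a model for analysis and that the toy data show the actual method, while 1.4 points to an equation number that does not exist.

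Second, the size depends on a design fact that the SAP does not give. Nothing in the documents supports four sequences. The three example orders in 1.3 could not all belong to one Latin square: two begin with A, and ABCD and BACD agree in periods 3 and 4. This stands. The four-sequence row is the worst case shown, and the range runs down to no loss. But independently drawn orders, a natural reading of the protocol, also lose power, so the problem does not rest on the worst case.

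Third, with one row per participant-period the error is conservative and the balanced treatment estimate is unbiased. That also stands: the cost is lost power and misreported precision, not false positives.

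Fourth, the row count concerns a different dataset of 15 subjects and shows no defect in this trial's data. That is fair; it supports only a request to state the row structure.

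**Conclusion.** The concern holds. The SAP contradicts itself on whether the primary treatment comparison includes a participant effect, and the model and code that an analyst would follow leave it out. With one value per participant per period, standard errors are overstated in every layout examined except the one where each completer has a distinct sequence label. At an ICC of 0.5, power falls from about 83% to 62% with four sequences and 69% with 12 labels, and from about 81% to 71% with independently drawn orders.

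These figures assume 24 complete participants, a difference of 0.85 within-participant SD and the stated ICC values; the SD multiple and the ICCs are not in the documents. The direction does not depend on those values as long as people differ and some share a label. Because this is the primary comparison, it should be settled before the data are analysed.

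**What to change.** **Essential**
- Name one governing model and correct the reference to (1.1) in SAP 1.4 and 2.1.
- Add a random participant intercept to (2.1), (2.2) and both copies of the code, for example ``(1 | `Subject ID`)``, with treatment and period fixed. This restores the participant term of the SAP's own model (3.1).
- Require one row per participant per period for each metabolite. Step 6 of the working shows why the intercept alone is not enough if there are several.

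**To settle in the same edit**
- State the number of randomised sequences. A fixed sequence effect is workable only if that number is small: 4 sequences leave 24 − 4 = 20 df for participant variance, and 24 orders leave 24 − 24 = 0.
- If sequence is kept, define it from all four visits and join by subject identifier. The appendix code uses two visits and binds the columns by row position.
- State whether treatment-by-period is kept. With a single four-sequence Latin square, fixed sequence, treatment, period and interaction need 1 + 3 + 3 + 3 + 9 = 19 columns, but there are only 4×4 = 16 sequence-by-period cells. Sequence and interaction cannot then both be fixed.
- Preferably fit by REML with Kenward-Roger or Satterthwaite df. This is a refinement, since maximum likelihood shrinks the standard error only by a factor of about 0.957.

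The cost is SAP and code wording. No additional participants, samples or data are needed.
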